Complete remission rate is defined as the proportion of subjects who achieve a CR. A Cochran Mantel-Haenszel (CMH) test will be used to compare CR rate between the 2 treatment arms. A logistic regression model will be used to estimate the treatment effect in terms of an odds ratio. The odds ratio and its associated 95% CIs will be presented.

Overall survival is defined as the time from date of randomization to the date of death due to any cause. Kaplan-Meier curves and KM estimates of OS will be presented for each treatment arm, including estimates of the median and other quantiles, as well as individual time points (eg, 3-, 6-, and 12-month rates). The log-rank test stratified by the randomization factors will be used to compare OS between the 2 treatment arms. The HR of OS with a 95% CI comparing the AG-120 + azacitidine arm with the placebo + azacitidine arm will be estimated from a Cox proportional hazards model stratified by the randomization stratification factors.

The CR + CRh rate is defined as the proportion of subjects who achieved a CR or CRh. CRh is defined as having all CR criteria except that ANC is $>0.5 \times 10^9/L$ ($500/\mu L$) and platelet count is $>50 \times 10^9/L$ ($50,000/\mu L$). Because CRh is not part of modified IWG response criteria, it will be derived by Sponsor. A CMH test will be used to compare the CR + CRh rate between the 2 treatment arms. A logistic regression model will be used to estimate the treatment effect in terms of an odds ratio. The odds ratio and its associated 95% CIs will be presented.

Objective response rate is defined as the rate of CR, CRi (including CRp), PR, and MLFS. The best response is calculated using the following hierarchy: 1) CR; 2) CRi (including CRp); 3) PR; and 4) MLFS. A summary of best response by treatment arm will be produced. A CMH test will be used to compare ORR between the 2 treatment arms. A logistic regression model will be used to estimate the treatment effect in terms of an odds ratio. The odds ratio and its associated 95% CIs will be presented.

Additional Secondary Endpoint Analyses:

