Current strategies for AML can be generally divided into intensive and non-intensive treatments. Intensive treatments are usually reserved for fit individuals and comprised of induction and consolidation chemotherapy and may also include allogeneic stem cell transplantation. The goal of intensive therapy is to achieve a long-term cure. In contrast, patients unable to receive intensive treatments may be treated with low-intensity therapies consisting of hypomethylating agents, blood product transfusions, and supportive care including antibiotics. The objective of low-intensity therapy is often palliative. The recommendation to treat a patient with intensive vs non-intensive treatment is individualized and incorporates the patient's age, de novo vs secondary nature of their AML, the presence of comorbidities, and other factors. Whereas intensive induction chemotherapy (IC) represents a standard of care for fit patients, the most appropriate treatment for older, unfit patients remains debatable. Unfit patients, typically including elderly patients with AML have an increased incidence of comorbidities (eg, cardiac and pulmonary dysfunction), poor hematologic reserves, and worse Eastern Cooperative

Oncology Group (ECOG) performance status (PS) due to age alone. Acute myeloid leukemia in this patient group is also more likely to be preceded by a myelodysplastic phase and has a higher incidence of unfavorable cytogenetic profiles than younger patients, known risk factors for poor outcome (Appelbaum et al, 2006; Döhner et al, 2017).

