7.1. Overall Study Design

Study AG120-C-009 is a global, Phase 3, multicenter, double-blind, randomized, placebo-controlled clinical trial to evaluate the efficacy and safety of AG-120 + azacitidine vs placebo + azacitidine in adult subjects with previously untreated IDH1m AML and who are considered appropriate candidates for non-intensive therapy. Up to 190 study centers in 20 countries will participate in this study.

Following provision of informed consent, all subjects will undergo Screening procedures within 4 weeks (28 days) prior to randomization to determine eligibility. Gene mutation analysis for confirmation of IDH1m disease from a bone marrow and germ-line mutation analysis from a buccal swab will be conducted for all subjects, and can be conducted prior to the 28-day Screening window. Central laboratory confirmation of IDH1m status is required for study eligibility. With Medical Monitor approval, subjects may be eligible and randomized with local IDH1m testing results; however, bone marrow aspirate for central laboratory testing must have been sent with proof of shipment to the central laboratory prior to randomization. In cases where bone marrow aspirate is not available (ie, dry tap), peripheral blood samples may be used for IDH1m confirmation with Medical Monitor approval. Additional Screening procedures include, but are not limited to: medical and medication history; bone marrow aspirate/biopsy for [REDACTED]; complete physical examination; vital signs; 12-lead ECG; ECOG PS; ECHO or MUGA scan for LVEF (method per institutional standard of care, with the same method used for an individual subject throughout the study; in Germany, only ECHO will be performed); clinical laboratory assessments (hematology, chemistry, coagulation, and serum pregnancy test); QoL assessments; and [REDACTED].

Subjects eligible for study treatment based on Screening assessments will be randomized 1:1 to receive oral AG-120 or matched placebo, both administered in combination with SC or IV azacitidine. Randomization will be stratified by de novo status (de novo AML and secondary AML) and geographic region (United States and Canada; Western Europe, Israel, and Australia; Japan; and rest of world).

An overview of the study design is provided in [Figure 1](#).

Figure 1: Schema for Study AG120-C-009

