12.13. Power for Analysis of Key Secondary Endpoints

12.13.1. Power for Analysis of Overall Survival

Overall survival will be compared between the 2 treatment arms, provided the primary endpoint of EFS is statistically significant favoring the AG-120 + azacitidine arm. Based on available data ([Dombret et al, 2015](#)), the median OS in the placebo + azacitidine arm is expected to be approximately 10.4 months. A target HR of 0.71 for OS (equivalent to a median OS of 10.4 months in the placebo + azacitidine arm vs 14.6 months in the AG-120 + azacitidine arm, assuming an exponential distribution) is assumed. Based on the 200 subjects planned to be enrolled in this study to detect the primary endpoint of EFS, it is estimated that at the time of the final analysis for EFS, approximately 145 deaths will be observed and this will provide 54% power at a 1-sided overall 2.5% level of significance to reject the null hypotheses (HR=1) using a log-rank test.

12.13.2. Power for Analysis of Complete Remission Rate, Complete Remission Plus Complete Remission with Partial Hematologic Recovery Rate, and Objective Response Rate

Based on a retrospective analysis of Study AZA-AML-001, the response rates in the placebo + azacitidine arm are expected to be approximately 20%, 25%, and 32% for CR rate, CR + CRh rate, and ORR, respectively. It is hypothesized that the AG-120 + azacitidine arm will result in an absolute 20% increase in the CR rate, CR + CRh rate, and ORR. Based on the 200 subjects planned to be enrolled in this study to detect the primary endpoint of EFS, the power for the analysis of each of these endpoints at a 1-sided 2.5% level of significance to reject the null hypotheses (odds ratio=1) using a CMH test are presented in [Table 13](#).

Table 13: Power for Analysis of CR Rate, CR + CRh Rate, and ORR

Endpoints	Number of Subjects	Target Response Rate (Azacitidine vs AG-120 + Azacitidine)	Power
CR rate	200	20% vs 40%	86%
CR + CRh rate	200	25% vs 45%	84%
ORR	200	32% vs 52%	81%

Abbreviations: CR = complete remission; CRh = complete remission with partial hematologic recovery; ORR = objective response rate; vs = versus.

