The treatment effects for the 2 components are clearly distinct and the assumption of proportional hazards will be violated. Therefore, instead of the overall HR, the assumptions for EFS are presented for the 2 components separately. Based on simulation results, the average overall HR over 10,000 simulations for the entire population is 0.641. However, the overall HR for the entire population was not part of the study design assumptions. Additionally, based on the current assumptions, for the overall population, the median EFS will be 1 day for both the placebo+azacitidine and AG-120+azacitidine arms.

Figure 2: Event-Free Survival under Protocol Assumptions

Abbreviations: EFS = event-free survival.

Under these assumptions, a total of 173 EFS events in approximately 200 randomized subjects with previously untreated IDH1m AML are required to provide 80% power at a 1-sided 2.5% level of significance to reject H_{01} using a stratified log-rank test (Table 3).

Table 3: Study Design Parameters for EFS

Design Parameters and Outcomes	
Power	80%
Significance level (1-sided)	2.5%
CR rate by 24 weeks (treatment vs control)	40% vs 20%
HR (treatment vs control) that can be detected for subjects who achieve CR by 24 weeks	0.76
Median EFS for subjects who achieve CR by 24 weeks (treatment vs control)	19.2 vs 14.6 months
Number of subjects randomized (1:1)	200
Target number of EFS events	173 EFS events
Accrual rate	3 subjects/month for the first 10 months, 5 subjects/month thereafter
Accrual time	44 months
Dropout rate	5%
Time to final analysis under H_{11}	52 months after first subject randomized

Abbreviations: CR = complete remission; EFS = event-free survival; HR = hazard ratio.

Overall Survival

Based on available data (Dombret et al, 2015), the median OS in the placebo+azacitidine arm is assumed to be 10.4 months. A target HR of 0.71 for OS (equivalent to a median OS of 10.4 months in the placebo+azacitidine arm vs 14.6 months in the AG-120+azacitidine arm, assuming an exponential distribution) is assumed. Based on 200 randomized subjects and the above assumptions, it is estimated that at the time of the final analysis for EFS, approximately 145 deaths will be observed. With 145 deaths, the study will have 54% power to detect a HR for OS of 0.71 at a 1-sided 2.5% level of significance using a stratified log-rank test.

CR, CR+CRh, and OR

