7.3.2. Disease Characteristics

The following baseline characteristics of the underlying disease will be summarized based on the data entered in the eCRF:

- Disease type
 - Nature of AML per Investigator [de novo; secondary (treatment-related AML; history of MDS; history of MPD; other)]
 - WHO classification of AML (AML with genetic abnormalities; AML with myelodysplasia-related changes; therapy-related myeloid neoplasms; AML not otherwise specified)
- ECOG PS at baseline (0; 1; 2; 3; 4)
- IDH1 mutation type at baseline based on central testing (R132C; R132G; R132H; R132L; R132S; wild type). Results from bone marrow will be used as the primary source. If results from bone marrow are not available, the results from peripheral blood will be used instead.
- IDH1 mutation status at baseline based on local testing (positive; negative)
- Cytogenetic results (normal karyotype; abnormal karyotype) and cytogenetic risk status according to the Investigator based on NCI NCCN guidelines (favorable; intermediate; poor; other)
- Baseline bone marrow aspirate blasts (%)
- Baseline bone marrow biopsy blasts (%)
- Baseline peripheral blood blasts (%)
- Baseline values of the following laboratory parameters. These parameters will be summarized as continuous variables as well as categorical variables using the specified category:
 - WBC (<15×10⁹/L; 15 to <30×10⁹/L; ≥30×10⁹/L)
 - ANC (<0.5×10⁹/L; 0.5 to <1×10⁹/L; ≥1.0×10⁹/L)
 - Hemoglobin (<80 g/L; ≥80 g/L)

- Platelet count ($<50 \times 10^9/L$; 50 to $<100 \times 10^9/L$; $\geq 100 \times 10^9/L$)
- Lactate dehydrogenase (LDH)
- Creatinine clearance (<15 mL/min; 15 to <40 mL/min; 40 to <60 mL/min; 60 to <90 mL/min; ≥ 90 mL/min)
- Extramedullary disease at baseline (yes; no; unknown; not assessed)

Data on disease characteristics will be provided in by-subject listings.

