7.7.2.2. Overall Survival

Overall survival is defined as the time from date of randomization to the date of death due to any cause. If a subject is not known to have died by the data cutoff date, then OS will be censored at the date of last contact (see [Section 6.3.7](#)).

If the primary analyses of EFS and CR rate are significant, OS will be tested using the log-rank test stratified by the randomization stratification factors at 1-sided 2.5% level of significance.

The HR will be estimated using a Cox's PH model stratified by the randomization strata. Each stratum will define a separate baseline hazard function (using the "STRATA" statement in SAS PROC PHREG), ie for the i -th stratum the hazard function is expressed as: $h(i;t)=h(i,0;t)\exp(x\beta)$, where $h(i,0;t)$ defines the baseline hazard function for the i -th stratum

and x defines the treatment arm (0=control arm, 1=treatment arm) and β is the unknown regression parameter. Ties will be handled by replacing the PH model by the discrete logistic model (Ties=Discrete option in SAS PROC PHREG).

Kaplan-Meier estimates (product-limit estimates) will be presented by treatment arm together with a summary of associated statistics including the median OS time with 2-sided 95% CIs. In particular, the OS rate at 3, 6, 9, 12, 18, 24 and 36 months will be estimated with corresponding 2-sided 95% CIs. The CIs for the median will be calculated according to Brookmeyer and Crowley and the CIs for the survival function estimates at the time points defined above will be derived using the log-log transformation (confotype=loglog default option in SAS PROC LIFETEST) with back transformation to a CI on the untransformed scale. The estimate of the SE will be computed using Greenwood's formula.

Frequency of subjects with an event (death) and censoring reasons will be presented by treatment arm. Reasons for censoring will be summarized according to the categories in Table 7 following the hierarchy shown.

Table 7: OS Censoring Reasons and Hierarchy

Hierarchy	Condition	Censoring Reason
1	No event and (EOS date \geq date of randomization when reason for EOS=Withdrawal by Subject)	Withdrawal of consent
2	No event and [(lost to follow-up in any disposition page or survival follow-up page) or (data cutoff date–last contact date >8 weeks)]	Lost to follow-up
3	No event and none of the conditions in the prior hierarchy are met	Alive

Abbreviations: OS=overall survival; EOS=end of study.

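### OS, with 54% stated power, is analysed without adjusting for cytogenetic risk, ECOG PS or age already collected at baseline; adjustment would help modestly but not make OS well powered

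*Protocol*

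**What the plan says.** **Test and estimate.** The Synopsis states: "The log-rank test stratified by the randomization factors will be used to compare OS between the 2 treatment arms". Protocol 12.5.2.1.2 says the same, and SAP 7.7.2.2 agrees: "OS will be tested using the log-rank test stratified by the randomization stratification factors at 1-sided 2.5% level of significance". Its Cox model has one regressor: "and x defines the treatment arm (0=control arm, 1=treatment arm) and β is the unknown regression parameter".

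**Strata.** Protocol 7.1: "Randomization will be stratified by de novo status (de novo AML and secondary AML) and geographic region". Region has four levels, so there are 2 x 4 = 8 cells.

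**Power.** Protocol 12.13.1: "approximately 145 deaths will be observed and this will provide 54% power at a 1-sided overall 2.5% level of significance". SAP 6.2.1 repeats it: "With 145 deaths, the study will have 54% power to detect a HR for OS of 0.71".

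**Prognosis.** Of AML in older, unfit patients, Protocol 5.1 says that it is more often preceded by a myelodysplastic phase and "has a higher incidence of unfavorable cytogenetic profiles than younger patients, known risk factors for poor outcome". Section 5.4.2 names the same two factors. Section 5.4.1 links age and poor ECOG PS to an especially poor prognosis.

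**Data.** Age and ECOG PS are baseline variables (SAP 7.3.1, 7.3.2), as is "cytogenetic risk status according to the Investigator based on NCI NCCN guidelines (favorable; intermediate; poor; other".

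**Other OS analyses.** Protocol 12.5.2 leaves sensitivity and subgroup analyses of the secondary endpoints to the SAP. The SAP's sensitivity list (7.7.1.2) and subgroup table (7.7.4) cover EFS only. The one OS supplement found is a per-protocol run (SAP Table 2). The subgroup section ends in redacted text, so this holds for the visible text.

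**The concern.** In a 200-subject trial, prognostic variation that is left in a survival comparison pulls the estimated hazard ratio toward 1 and costs power. It also leaves the comparison open to chance imbalance. Here the variables are already planned data, and the protocol itself calls one of them a known risk factor.

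The position of OS raises the stakes. CR+CRh and ORR have stated powers of 84% and 81%, but each is tested only if OS succeeds. The chance of a confirmatory claim on either is therefore capped by the power of OS. The SAP does prespecify baseline adjustment elsewhere: its QLQ-C30 mixed model includes the baseline score.

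**Working it through.** **1. Reproduce the stated power.** Inputs from Protocol 12.13.1: 145 deaths, HR 0.71, 1:1 allocation, 1-sided 2.5%.

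Power = Φ(½ √145 × ln(1/0.71) − 1.960) = Φ(6.021 × 0.3425 − 1.960) = Φ(0.102) = 54.1%.

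The 54% reproduces. The formula has no term for strata or covariates. With exponential OS (medians 10.4 and 14.6 months), the stated accrual (30 + 170 = 200), a month-52 cutoff and an assumed dropout hazard of 0.003 per month, expected deaths are 144.5, against 145 stated.

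**2. Compare the planned eight-cell test with an adjusted test.** The documents give no prevalence or prognostic strength for this population, so these are assumptions:
- poor cytogenetics 25%, ECOG PS 2 40%, age ≥75 50%, independent of one another;
- secondary AML 25% (death HR 1.0 to 1.5);
- regional shares 15/45/10/30%.

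The treatment effect is set so that the unadjusted HR is about 0.71. There are 6,000 simulated trials per row. The adjusted test is the Wald test of treatment in a Cox model with the same eight strata plus the three covariates.

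| Death HR: cytogenetics / ECOG / age | Planned log-rank | Adjusted | Difference (points) |
|---|---|---|---|
| 1.0 / 1.0 / 1.0 | 49.6% | 49.3% | −0.3 |
| 1.25 / 1.25 / 1.25 | 50.6% | 51.0% | +0.4 |
| 1.5 / 1.5 / 1.5 | 50.4% | 53.4% | +3.0 |
| 2.0 / 1.5 / 1.5 | 49.8% | 55.2% | +5.4 |
| 2.0 / 2.0 / 1.5 | 49.5% | 57.2% | +7.7 |
| 2.5 / 2.0 / 2.0 | 49.9% | 61.3% | +11.4 |

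The unstratified log-rank test in the same trials had 52.5% to 54.8% power. The planned test falls to about 50% because some of the eight cells are small under the assumed shares.

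Two further simulations, also against the eight-cell test, agree:
- HRs 1.5/1.2/1.1 (age per 10 years): 49.4% to 50.7%. HRs 2.0/1.4/1.2: 51.9% to 55.3%.
- A separate run gave gains of about 2, 4 and 8 points for weak, moderate and strong effects, from about 50-56% to 52-63%.

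**3. Cross-check.** If the covariates explain a share R² of the variation, effective deaths are about 145/(1 − R²). For R² of 5, 10, 15 and 20% this gives 153, 161, 171 and 181 deaths. Step 1's formula then gives 56%, 58%, 61% and 63%.

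**4. Distance from adequate power.** Deaths needed for 80% = 4 × (1.960 + 0.842)² / 0.3425² = 268.

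**5. Type I error.** Under no treatment effect, the adjusted Wald test rejected in 2.5% to 2.9% of trials and the planned test in 2.3% to 2.8% (Monte Carlo SE 0.2 points). The separate run found 2.5% for the adjusted test.

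**6. Chance imbalance.** With 25% poor risk and 100 per arm, the SE of the difference is √(2 × 0.25 × 0.75/100) = 0.061. A 10-point difference has z = 1.63: probability about 10% in either direction, about 5% in the harmful one. To first order, with a death HR of 2.0, it shifts the log HR by 0.10 × ln 2 = 0.069, which moves 0.71 to about 0.76, or about as far the other way.

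**The case against.** The other side is substantial, and several parts of it stand.

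- **The planned test is conventional and valid.** It matches the randomization, protocol and SAP agree on it, and the low power is openly stated. A reader might infer that the OS test is biased or has the wrong error rate. It does not: randomization covers imbalance in both directions.
- **Prognosis is not ignored.** One of the two risk factors that the protocol names, an antecedent myelodysplastic phase, is largely carried by the de novo/secondary stratum, because history of MDS is coded as secondary AML. Cytogenetics, ECOG PS and age remain outside.
- **Prognostic strength here is unknown.** The protocol's statements contrast older or unfit patients with younger ones and do not describe IDH1-mutated subjects. Covariates may also be correlated: Inclusion Criterion 1 admits subjects for age ≥75 or ECOG PS 2, which links the two negatively. Allowing for correlation between cytogenetics and secondary AML left a moderate gain of 3.7 points (49.9% to 53.6%). Adding the eligibility link left 2.8 (50.6% to 53.4%). The gain shrinks but remains.
- **The estimand shifts.** The SAP's OS hypothesis concerns the arms' survival functions, whereas an adjusted Cox HR is conditional (0.66 to 0.70 in step 2 when the unadjusted HR is about 0.71). This stands and shapes the fix.
- **The statistic matters.** If the true Wald size were 2.9%, that alone would be worth about 2.5 points of power. This favours a score or covariate-adjusted log-rank test.
- **Data quality cannot be judged.** Cytogenetic risk is investigator-assessed with an 'other' level, and the protocol's cytogenetics section is redacted.

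**Conclusion.** The point holds as a modest, nearly free improvement. No visible OS analysis uses three baseline variables that the trial collects and the protocol links to outcome. Adjustment would add about 1-2 points of power for weak effects, 3-5 for moderate and 7-11 for strong, over a planned test at about 50-56%. These sizes rest on assumed prevalences, cell sizes and prognostic strengths; with very weak effects the gain is close to zero.

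Two stronger readings are tempting. One is that the 54% results from the missing adjustment, or that adjustment would make OS well powered. The documents do not support this: the 54% follows from 145 deaths and HR 0.71 alone, and 80% would need 268 deaths. The other is that the gain should be counted upward from 54%. That figure takes no account of strata, while both the planned and the adjusted tests are stratified in eight cells, so the comparison must be made there.

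**What to change.** Before unblinding, amend the Synopsis, Protocol 12.5.2.1.2 and SAP 7.7.2.2 as follows.

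1. Make the confirmatory OS test a 1-sided, covariate-adjusted test stratified by de novo status and region: either a score test from the stratified Cox model or a covariate-adjusted log-rank test. The latter keeps the marginal null hypothesis. Name the statistic.
2. Fix the covariates and coding: cytogenetic risk (poor vs not poor, with a category for other or missing), ECOG PS (0-1 vs 2) and age (continuous).
3. Keep the treatment-only stratified HR and the Kaplan-Meier estimates as the marginal summary. Report the adjusted HR with its 95% CI beside them, labelled conditional.
4. If the sponsor keeps the stratified log-rank test as confirmatory, or unblinding has occurred, add the adjusted analysis to the SAP as an OS sensitivity analysis, which Protocol 12.5.2 already foresees.

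The cost is wording and programming, with no new data or patients. The downsides are a conditional HR to explain, a category for missing or other cytogenetics, and a loss of up to about 1 point of power if the covariates are not prognostic.
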